7.7.2 Rescue Therapy

Participants having intolerable symptoms within the first 4 weeks of treatment may use the below topical agents (according to their respective label instructions) as rescue therapy up until Week 4 according to the investigator's judgement.

- Fluocinolone acetonide 0.025%
- Hydrocortisone butyrate 0.1%
- Mometasone furoate 0.1%
- Triamcinolone acetonide 0.1%

Participants requiring and completing ≤ 7 days of topical rescue therapy within the first 4 weeks of IP treatment initiation, will remain eligible to be counted as responders for categorical efficacy endpoints; their numerical endpoints will also be counted as if they did not receive rescue therapy.

Participants either (1) requiring topical rescue therapy after 4 weeks of IP treatment, or for more than 7 days, or (2) requiring systemic corticosteroid/immunosuppression or phototherapy will discontinue from study treatment and be considered treatment failures for categorical endpoints.

Participants who discontinue study treatment are to remain in the study and complete all study visits and assessments unless they withdraw consent ([Section 8.2](#)).

Statistical handling of data from participants requiring rescue medication appears in [Section 10.3.1](#).

7.7.3 Use of Concomitant Emollient

Application of fixed doses of an additive-free, basic bland emollient twice-daily for ≥ 7 days before baseline visit and for the duration of the study is required.

Note: On study visit days, showering or bathing is permitted prior to attending the study visit, but participants must not moisturize or apply emollient. The additive-free, basic bland emollient is allowed after the visit.

7.8 Treatment After the End of the Study

At the end of the study, BMS will not continue to provide BMS supplied study treatment to participants/investigators unless BMS chooses to extend the study. The investigator should ensure that the participant receives appropriate standard of care to treat the condition under study.

BMS reserves the right to terminate access to BMS supplied study treatment if any of the following occur: a) the study is terminated due to safety concerns; b) the development of the study treatment is terminated for other reasons, including but not limited to lack of efficacy and/or not meeting the study objectives; c) the participant can obtain medication from a government sponsored or private health program. In all cases BMS will follow local regulations.

8 DISCONTINUATION CRITERIA

8.1 Discontinuation from Study Treatment

Participants MUST discontinue investigational product (and non-investigational product at the discretion of the investigator) for any of the following reasons:

- Participant's request to stop study treatment. Participants who request to discontinue study treatment will remain in the study and must continue to be followed for protocol specified follow-up procedures. The only exception to this is when a participant specifically withdraws consent for any further contact with him/her or persons previously authorized by participant to provide this information
- Any clinical adverse event (AE), laboratory abnormality or intercurrent illness which, in the opinion of the investigator, indicates that continued participation in the study is not in the best interest of the participant
- Termination of the study by Bristol-Myers Squibb (BMS)
- Loss of ability to freely provide consent through imprisonment or involuntary incarceration for treatment of either a psychiatric or physical (eg, infectious disease) illness. (Note: Under specific circumstances and only in countries where local regulations permit, a participant who has been imprisoned may be permitted to continue as a participant. Strict conditions apply and BMS approval is required.)
- Asthma or COPD that requires systemic glucocorticoid or biologic treatment, or inhaled budesonide or equivalent at >1200 µg/day or fluticasone propionate at > 880 µg/day along with another anti-asthma/COPD drug such as a long-acting beta-agonist.
- Systemic or photo-based rescue therapy for AD ([Section 7.7.2](#)),
- Replication-competent (live) vaccine
- Grade 4 lymphopenia (ALC < 200) with repeat testing within 7 days (according to the Common Toxicity Criteria for Adverse Events [CTCAE] version 5.0)
- Elevation of ALT or AST > 5x ULN or concurrent elevations of ALT or AST > 3x ULN and bilirubin > 2x ULN
- Decline in PFT values (FEV1 and/or FVC) below 30% of the baseline values
- Diagnosis of macular edema, retinal or choroidal disease or syndrome
- Grade 2 or higher cardiac or bone marrow adverse events (with exception of ALC) according to the CTCAE version 5.0.
- Grade 3 for other system adverse events (according to the CTCAE version 5.0)
- Missed dose of ≥ 3 consecutive days or overall compliance < 85% over a period of > 30 days starting from study Day 1.

Refer to the [Schedule of Activities](#) for data to be collected at the time of treatment discontinuation and follow-up and for any further evaluations that can be completed

In the case of pregnancy, the investigator must immediately, within 24 hours of awareness of the pregnancy, notify the BMS Medical Monitor/designee of this event. In most cases, the study treatment will be permanently discontinued in an appropriate manner (eg, dose tapering if necessary for participant safety). Refer to [Section 9.2.5](#) Pregnancy.

All participants who discontinue study treatment should comply with protocol specified follow-up procedures as outlined in [Section 2](#). The only exception to this requirement is when a participant withdraws consent for all study procedures including post-treatment study follow-up or loses the ability to consent freely (ie, is imprisoned or involuntarily incarcerated for the treatment of either a psychiatric or physical illness).

If study treatment is discontinued prior to the participant's completion of the study, the reason for the discontinuation must be documented in the participant's medical records and entered on the appropriate case report form (eCRF) page.

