Abbreviations: AD = Atopic Dermatitis; BSA = Body Surface Area; CBC = Complete Blood Count; COVID-19 = coronavirus disease 2019; CXR = Chest X-ray; DLCO = Diffusion Capacity; DLQI = Dermatology Life Quality Index; EASI = Eczema Area and Severity Index; ECG = electrocardiogram; eCRF = Electronic Case Report Form; eGFR = estimated Glomerular Filtration Rate; FEV1 = Forced Expiratory Volume in 1 second; FVC = Forced Vital Capacity; FSH = Follicle Stimulating Hormone; HBcAb = Hepatitis B core antibody; HBsAb = Hepatitis B surface antibody; HBsAg = Hepatitis B surface antigen; HCV = Hepatitis C virus; HIV = Human Immunodeficiency virus; ICF = Informed Consent Form; INR = international normalized ratio; IRT = Interactive Response Technology; LH = Luteinizing hormone; NRS = Numerical Rating Scale; PA = Posteroanterior; POEM = Patient Oriented Eczema Measure; PPE = Personal Protective Equipment; PT = prothrombin time; RT-PCR = Reverse transcriptase polymerase chain reaction; SAE = Serious Adverse Event; SARS-CoV-2 = severe acute respiratory syndrome coronavirus 2; TB = Tuberculosis; UA = urinalysis; vIGA-AD = validated Investigator Global Assessment scale for Atopic Dermatitis; WOCBP = Women of Childbearing Potential.

Table 2-2: On-treatment Procedural Outline (IM018005)

Procedure	Day 1 ^a (Rand)	Day 8 W1 (± 1 days)	Day 15 W2 (± 3 days)	Day 29 W4 (± 3 days)	Day 57 W8 (± 3 days)	Day 85 ^a W12 (± 3 days)	Day 113 (EOT) W16 (± 3 days)	Notes
Administrative and Historical Assessments								
Inclusion/Exclusion Criteria	X							Review of inclusion/exclusion criteria that are specified on or defined relative to the randomization day
Randomization via IRT	X							
Disease/Efficacy Assessment								
EASI	X	X	X	X	X	X	X	EASI at baseline must be ≥ 16 (prior to randomization).
vIGA-AD	X	X	X	X	X	X	X	
BSA Assessment	X	X	X	X	X	X	X	
Pruritus and Sleep Quality NRS	X	X	X	X	X	X	X	Will be collected daily in an electronic diary – represents preceding 24 hours. Data will be collected at each specified visit.
DLQI	X	X	X	X	X	X	X	Data will be collected at each specified visit.
POEM	X	X	X	X	X	X	X	
PGI-S	X	X			X		X	
PGI-C		X			X		X	
Pulmonary Function Test				X			X	FEV1, FVC & DLCO may be collected within a window of ± 5 days of visit.
Visual Acuity Testing and Optical Coherence Tomography					X		X	May be collected within a window of ± 7 days of visit.
Safety Activities								
Body Weight	X						X	

Table 2-2: On-treatment Procedural Outline (IM018005)

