5.1.2 Treatment Period, Days 1-113

On Day 1, eligible participants will be randomly allocated to receive one of: placebo, BMS-986166 0.25 mg PO QD, BMS-986166 0.5 mg PO QD, BMS-986166 0.75 mg PO QD, or branebrutinib 9 mg PO QD for 16 weeks. Randomization will be in a 1:1:1:1:1 ratio. Blinded treatment assignment will be managed by Interactive Response Technology (IRT).

Participants will visit the clinic 7 times (including baseline) during the treatment period. Safety and efficacy will be assessed at each of these visits. This visit density is intended to allow monitoring of sufficiently high resolution to detect infections, excessively low leukocyte counts, inefficacy and/or flares, and other problems in a timely fashion; with on the other hand, participant burdens and risk of SARS-CoV-2 (severe acute respiratory syndrome coronavirus 2) exposure associated with clinic visits. This frequency reflects customary practice in the field as reflected in other published studies.³¹

Participants may receive topical rescue therapy for intolerable symptoms up to Week 4 as described in [Section 7.7.2](#). After Week 4, participants receiving rescue treatments will be considered treatment failures for categorical endpoints, those who require systemic rescue therapy will be immediately discontinued from study treatment.

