6.2 Exclusion Criteria

1) Medical Conditions

- a) Any major illness/condition or evidence of an unstable clinical condition (eg, cardiac, renal, hepatic, hematologic, gastrointestinal, endocrine, pulmonary, neurologic, immunologic, psychiatric) or local active infection/infectious illness that, in the investigator's judgment, will substantially increase the risk to the participant if he or she participates in the study or interfere with the interpretation of study results.
- b) Pregnancy, lactation, or plans for either during the study or the post-study prohibition period (see [Inclusion Criteria](#) for prohibition period duration).
- c) Clinically relevant cardiovascular conditions, including history or presence of:
 - i) Recent (within the last 6 months) occurrence of myocardial infarction, unstable angina, stroke, transient ischemic attack, decompensated heart failure requiring hospitalization, sick sinus syndrome, Class III/IV heart failure ([Appendix 6](#))
 - ii) Prolonged QTcF interval (QTcF > 450 msec males, > 470 msec females), or at additional risk for QT prolongation (eg, hypokalemia, hypomagnesemia, congenital long-QT syndrome)
 - iii) Any prior history of atrial fibrillation or flutter
 - iv) Treatment with Class Ia or Class III anti-arrhythmic drugs or treatment with 2 or more agents in combination known to prolong PR interval
 - v) Patients with other pre-existing stable cardiac conditions who have not been cleared for the study by an appropriate cardiac evaluation by a cardiologist
- d) Clinically relevant pulmonary conditions, including:
 - i) Unstable asthma or chronic obstructive pulmonary disease (COPD) (eg, acute episodes of exacerbation [nocturnal episodes, sudden episodes triggered by unidentifiable factors] despite a stable regimen of relevant medications); prior episode(s) of life-threatening asthma or COPD; or asthma or COPD that requires systemic glucocorticoid or biologic treatment, or inhaled budesonide or equivalent at > 1200 µg/day or fluticasone propionate at > 880 µg/day along with another anti-asthma/COPD drug such as a long-acting beta-agonist.
 - ii) Severe untreated sleep apnea
 - iii) Forced expiratory volume (FEV1) or forced vital capacity (FVC) < 70% of predicted values at screening

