If participants have elevations in ALT and/or AST \geq 3x the upper limit of normal (ULN), a retest should be performed as soon as possible but not later than 4 days after the original test. If the abnormality is confirmed, twice-weekly testing should occur until ALT and AST are < 3x ULN. If the ALT and/or AST stabilizes at a level > 3x ULN, the Medical Monitor may agree to less frequent testing. Other liver-related laboratory testing, including international normalized ratio (INR), alkaline phosphatase (AP), gamma-glutamyl transferase (GGT), hepatitis serologies, and other tests as deemed necessary by the investigator should be performed to better understand the observation.

The investigator should establish causality. In addition, the confirmed elevation $> 3x$ ULN is an AEI (see [Section 9.2.8](#)) and should be reported by the investigator. At any time, if any of the following occur and there are no apparent alternative causes for the finding, the investigational drug must be permanently discontinued:

- ALT or AST $> 8x$ ULN or
- ALT or AST $> 5x$ ULN with confirmation, within 2 weeks or
- ALT or AST $> 3x$ ULN and (total bilirubin $> 2x$ ULN or INR > 1.5) or
- ALT or AST $> 3x$ ULN with the appearance of fatigue, nausea, vomiting, right upper quadrant pain or tenderness, fever, rash, and/or eosinophilia ($>5\%$).

The investigator should establish causality. After discontinuation due to elevation of ALT or AST $> 5x$ ULN or concurrent elevations of ALT or AST $> 3x$ ULN and bilirubin $> 2x$ ULN, further liver function evaluation should be performed (for example, coagulation panel and alkaline phosphatase) in consultation with the Medical Monitor.

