An initial sharp decrease followed by a slow progressive decline over time in FEV1 was observed in fingolimod clinical studies. Nonclinical toxicity studies however with BMS-986166 have not revealed the potential for pulmonary toxicity at doses considerably higher than the pharmacologically active dose. PFTs including FEV1, FVC, and diffusion capacity of carbon monoxide (DLCO), will be measured in all participants. Every participant whose PFTs are abnormal will be followed until such time as resolution is confirmed or no further improvement is expected by the investigator.

Any condition that might affect the outcome of pulmonary function testing including infection, respiratory symptoms, occupational exposures (including asbestos) and cigarette smoking needs to be collected before PFT testing and transcribed to the PFTs eCRF page. If participants experience a decline in PFT values (FEV1 and/or FVC) below 30% of the baseline values, treatment should be discontinued.

If a participant discontinues due to a respiratory AE, the investigator should ensure that the patient has adequate evaluations as clinically indicated by a pulmonologist for the AE. Further evaluations will be conducted until such time as resolution is confirmed or no further improvement is expected by the investigator (based on a follow-up period of not less than 3 months).

- **Hepatotoxicity:**

Fingolimod caused frequent, reversible liver enzyme elevations greater than 3-fold above the ULN in up to 12% of patients; this was a significant cause of cessation of therapy. In this study, clinical blood chemistry analyses to assess liver function tests (LFTs) will be performed. Every patient whose LFTs are abnormal will be followed until values return to baseline.

Refer to [Section 9.2.6](#) and [Section 9.2.7](#) for instructions regarding hepatotoxicity.

- **Macular edema:**

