9.4.5 Pulmonary Function Tests

Pulmonary findings in animals and humans are associated with full-agonist S1PR1 modulators such as fingolimod.^{120,121} It is hypothesized that the differentiated biased-ligand properties of BMS-986166 ([Section 3.2.1.1](#)) obviates this phenomenon and its downstream consequences such as pulmonary effects and macular edema in animals and humans; this hypothesis is supported by observations in nonclinical models.³⁸

- In both Studies IM018001¹²² and IM018003,¹²³ there was no apparent effect of BMS-986166 on pulmonary function including FVC, FEV1, or DLCO. Participants underwent frequent safety assessments while in the clinic and during an extended follow-up period to monitor for AEs. Decline in PFT values (FEV1 and/or FVC) below 30% of the baseline values during treatment in this study (IM018005) will result in discontinuation from further study drug administration.

To monitor the potential pulmonary effects of BMS-986166, FEV1, FVC, and DLCO measurements will be performed as indicated the Schedule of Activities (Section 2). These tests will be performed at a qualified pulmonary function laboratory or respiratory department. Please refer to the American Thoracic Society/European Respiratory Society guidelines for standardization of spirometry and single breath determination of carbon monoxide uptake in the lung.^{124,125,126}

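### As written in three sections, the mandatory lung-function stop acts only when FEV1 or FVC falls under 30% of baseline; a fall of more than 30% was probably meant

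*Combined protocol and SAP*

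**What the plan says.** **Lung.** Section 8.1 makes the following a mandatory reason to stop study drug: "Decline in PFT values (FEV1 and/or FVC) below 30% of the baseline values". Section 9.2.8, under pulmonary effects, says "If participants experience a decline in PFT values (FEV1 and/or FVC) below 30% of the baseline values, treatment should be discontinued". Section 9.4.5 attaches the same consequence to a "Decline in PFT values (FEV1 and/or FVC) below 30% of the baseline values during treatment in this study". No other section gives an on-treatment limit for FEV1 or FVC. At entry, section 6.2 excludes "Forced expiratory volume (FEV1) or forced vital capacity (FVC) < 70% of predicted values at screening".

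Pulmonary function is tested at screening (Table 2-1), then on Day 29 and Day 113 (Table 2-2), and again at Day 169 or study withdrawal (Table 2-3). The Table 2-2 note reads "FEV1, FVC & DLCO may be collected within a window of" ±5 days of the visit. Dosing is daily; section 5.1.2 gives, for example, "branebrutinib 9 mg PO QD for 16 weeks".

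**Liver.** Section 8.1 also requires a stop for "Elevation of ALT or AST > 5x ULN or concurrent elevations of ALT or AST > 3x ULN and bilirubin > 2x ULN". Section 9.2.6 has its own list, introduced by "if any of the following occur and there are no apparent alternative causes for the finding, the investigational drug must be permanently discontinued". Its four criteria are:
- ALT/AST above 8x ULN;
- above 5x ULN, confirmed within 2 weeks;
- above 3x ULN with total bilirubin above 2x ULN or INR above 1.5;
- above 3x ULN with listed symptoms, rash or eosinophilia above 5%.

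Section 9.2.6 also blinds total WBC and differential results during treatment. Sites are notified only of ALC below 200, ANC below 1000 or total WBC above 20,000 cells/µL.

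**The concern.** The lung rule is a mandatory safety stop for an effect that section 9.2.8 monitors as a class risk, citing an early sharp fall in FEV1 with fingolimod. A limit of 30% of baseline is a loss of more than 70%, which is implausible as a safety threshold. The common form of such a rule is a fall of 30%, and the wording looks like a slip from one to the other. Because all three sections use the same phrase, a site cannot resolve the doubt by reading elsewhere. Section 9 allows no protocol waivers, so sites are expected to follow the text.

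Two lesser points concern the liver criteria. The plan has two lists and does not say how they relate. One trigger in the second list depends on a laboratory result that the site does not receive.

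**Working it through.** The plan states no figure that this point could reproduce. The check is threshold arithmetic and a comparison of sections.

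**1. The two readings of the lung rule.** Inputs are the limit in 8.1 and the 70%-of-predicted entry floor in 6.2. The screening test is taken as baseline, being the only test scheduled before dosing.
- Literal: stop below 0.30 × baseline, a loss of more than 1 − 0.30 = 70%.
- Probable intent: stop below 0.70 × baseline, a loss of more than 30%.

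| Baseline, % of predicted | Literal: stop below | Fall of more than 30%: stop below |
|---|---|---|
| 70 | 0.30 × 70 = 21 | 0.70 × 70 = 49 |
| 80 | 0.30 × 80 = 24 | 0.70 × 80 = 56 |
| 100 | 0.30 × 100 = 30 | 0.70 × 100 = 70 |

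The readings give opposite answers for any value from 30% up to, but not including, 70% of baseline. A participant at 50% of baseline is in that band.

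**2. When the rule can act.** Sixteen weeks is 16 × 7 = 112 daily doses, Day 1 to Day 112. This agrees with Table 9.5.1-1, which labels the Day 113 sample 24 hours post-dose. The scheduled on-treatment tests are Day 29 and Day 113. The second is the end-of-treatment visit, when there is no dosing left to stop. With the 5-day window it could fall on Day 108, with at most 112 − 108 + 1 = 5 doses remaining. Day 29 is therefore the one scheduled test, before end of treatment, at which the rule can act.

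**3. The liver lists.** The same cases were run through each list, and then through both together (stop if either is met).

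| Case | 8.1 | 9.2.6 list | Either |
|---|---|---|---|
| ALT 6x, unconfirmed | stop | no | stop |
| ALT 6x, confirmed, alternative cause | stop | no | stop |
| ALT 9x, alternative cause | stop | no | stop |
| ALT 4x, bilirubin 2.5x, alternative cause | stop | no | stop |
| ALT 4x, INR 1.6, no alternative cause | no | stop | stop |
| ALT 4x with symptoms, no alternative cause | no | stop | stop |
| ALT 4x alone | no | no | no |

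Taken separately, the lists differ in both directions. Taken together, they give one answer for every case. The cost is that the criteria above 8x and confirmed above 5x add nothing, since both lie inside the 8.1 criterion of above 5x.

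**4. The eosinophil trigger.** The last criterion in 9.2.6 counts eosinophilia above 5%. That result comes from the differential, which is blinded on treatment, and it is not among the three results that sites are told about. A site cannot act on that element.

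**The case against.** **Lung.** The best defence is that no participant depends on this sentence alone. Section 9.2.8 requires follow-up of every participant with abnormal tests. Section 9.2.9 requires significant worsening on a safety assessment to be recorded as an adverse event. Section 8.1 then offers stops for investigator judgement, Grade 3 events and escalation of asthma or COPD treatment. Section 9 requires immediate discussion of safety concerns with the sponsor. Section 9.4.5 reports no apparent effect on FVC, FEV1 or DLCO in either Phase 1 study of BMS-986166. All of this stands, and it lowers the likely harm. None of it supplies a numeric FEV1 or FVC limit.

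A reader might infer that someone at half of baseline on Day 29 would take the remaining 112 − 29 + 1 = 84 doses, or 84/112 = 75% of the course, before anyone looked again. The documents do not support that. The count treats the lung criterion as the only safeguard and ignores the provisions just listed.

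**Liver.** A reader might infer that the two lists give sites contradictory orders, so that one site stops at an unconfirmed 6x and another properly waits. That does not hold. Section 8.1 requires a stop for any one listed reason, with no confirmation step and no exception for alternative causes. Section 9.2.6 nowhere tells sites to continue drug, and its closing paragraph refers to discontinuation at the 8.1 thresholds without asking for confirmation. The lists work as a union with redundant criteria. A reader might also think that the INR criterion cannot operate because PT/INR is a screening-only test in section 9.4.9. However, 9.2.6 already calls for INR among the further tests when enzymes rise. Whether an alternative cause should excuse the INR criterion is a clinical choice for the sponsor.

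The eosinophil point is narrow: the other findings in that criterion are symptoms or signs that a site can observe.

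**Conclusion.** The lung rule is wrong as written and must be corrected. Literally it requires a loss of more than 70%, below 21% of predicted at the entry floor, where a fall of more than 30% (below 49%) was probably meant. That the wording is defective rests on the text alone. The 30% fall is an inference about intent, which the sponsor has to confirm. The predicted-value figures assume that the screening test serves as baseline. The number of participants affected cannot be derived from the documents.

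The liver points are secondary and worth fixing. The plan lacks a sentence saying that the lists are additive, and one trigger is invisible to sites. Neither amounts to conflicting instructions.

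**What to change.** **Must fix.** In 8.1, 9.2.8 and 9.4.5, replace the lung criterion with: *a decline of more than 30% from baseline in FEV1 and/or FVC (value <70% of baseline)*, with the sponsor confirming that this is the intent.

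**Should fix.**
- In 9.2.6, state that its liver criteria add to the 8.1 stops, and that an unconfirmed ALT/AST above 5x ULN stops drug under 8.1.
- Add ALT/AST above 3x ULN with eosinophils above 5% to the centrally notified results in 9.2.6. The existing alternative-cause condition stays; it matters here because section 3.1.1 links atopic dermatitis itself with eosinophilia. The alert need not disclose the lymphocyte count.

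**Cost.** Wording in four sections, one conditional laboratory alert on blood already drawn, and a note to sites. No added visits, participants or change to the analysis.

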9.2.6 Laboratory Test Result Abnormalities

The following laboratory test result abnormalities should be captured on the nonserious AE CRF page or SAE Report Form electronic, as appropriate. Paper forms are only intended as a back-up option when the electronic system is not functioning.

- Any laboratory test result that is clinically significant or meets the definition of an SAE
- Any laboratory test result abnormality that required the participant to have study treatment discontinued or interrupted
- Any laboratory test result abnormality that required the participant to receive specific corrective therapy

It is expected that wherever possible, the clinical rather than laboratory term would be used by the reporting investigator (eg, anemia versus low hemoglobin value).

Clinically significant changes, in the judgment of the investigator, in laboratory parameters (abnormalities) will be recorded as AEs. During the treatment period, all total WBC and WBC differential results will be blinded. Reductions in ALC levels is a known PD effect of BMS-986166. If any of the following results are observed, the investigator will be notified and asked to repeat the laboratory tests within approximately 7 days:

- Absolute lymphocyte count [ALC] < 200 cells/ μ L
- Absolute neutrophil count [ANC] < 1000 cells/ μ L
- Total WBC > 20,000 cells/ μ L

If the repeat values also exceed these limits, the investigator will be informed that the patient's results for the abnormal parameter have fallen below the acceptable threshold.

If ANC or total WBC counts are confirmed below the acceptable limits, the Medical Monitor will contact the treating investigator to request close monitoring for risk of serious infection and appropriate follow-up, at the discretion of the investigator.

If the ALC is confirmed < 200 cells/ μ L, the investigator will discontinue investigational drug and then consult with the Medical Monitor. Laboratory testing will be repeated weekly until ALC is > 500 cells/ μ L.

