9.4.9 Clinical Safety Laboratory Assessments

Investigators must document their review of each laboratory safety report.

A central laboratory will perform the analyses and will provide reference ranges for these tests. WBC counts and lymphocyte counts will be monitored centrally and will not be provided to the site to prevent potential unblinding of the investigator.

Results of clinical laboratory tests performed on Day -1 must be available prior to dosing.

Hematology	
Hemoglobin	
Hematocrit	
Total leukocyte count, including differential	
Platelet count	
Coagulation Panel	
Prothrombin time/International normalized ratio (PT/INR)- screening only	
Chemistry	
Aspartate aminotransferase (AST)	Total Protein
Alanine aminotransferase (ALT)	Albumin
Total bilirubin	Sodium
Direct bilirubin	Potassium
Alkaline phosphatase	Chloride
Lactate dehydrogenase (LDH)	Calcium
Creatinine	Phosphorus
Blood Urea Nitrogen (BUN)	Magnesium
Uric acid	Creatine phosphokinase
Fasting glucose	eGFR calculation
Cholesterol & Lipid Panel	Hemoglobin A1c
Testosterone	Follicle-stimulating hormone (FSH)
	Luteinizing hormone (LH)
Urinalysis	
Protein	
Glucose	
Blood	
Leukocyte esterase	
Specific gravity	
pH	
Microscopic examination of the sediment if blood, protein or leukocytes esterase are positive on the dipstick	
Screening Serology	
Serum for hepatitis C antibody, hepatitis B surface antigen, hepatitis B core antibody, HIV-1 and -2 antibody (screening only)	
Other Analyses	
Test for drugs of abuse (urine or serum), (screening and predose on Day 1)	
Pregnancy test (WOCBP only).	
Follicle stimulating hormone (FSH) (screening only for select women only)	
QuantiFERON-TB Gold test (or equivalent if not available; screening only)	
SARS-CoV-2 serology test	
SARS-CoV-2: RT-PCR Test or Antigen test	

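### The Section 8.1 mandatory stop for Grade 2 or higher bone marrow events is not carried into Section 9.2.6, the only described route by which a blinded site learns of a low neutrophil count

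*Combined protocol and SAP*

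**What the plan says.** Section 8.1 lists the reasons for which a participant must come off investigational product. One is "Grade 2 or higher cardiac or bone marrow adverse events (with exception of ALC) according to the CTCAE version 5.0". The protocol does not define a bone marrow event and attaches no neutrophil count to this bullet. Lymphocytes have their own bullet (ALC below 200, with a repeat within 7 days).

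Section 9.2.6 sets out how blood counts reach the site. "During the treatment period, all total WBC and WBC differential results will be blinded", and Section 9.4.9 adds that "WBC counts and lymphocyte counts will be monitored centrally and will not be provided to the site". The investigator is notified, and asked to repeat the test within about 7 days, if ALC is below 200, ANC is below 1000 or total WBC is above 20,000 cells/µL. If the repeat agrees, the investigator is told that the parameter is outside its limit. The next step depends on the parameter:

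- ANC: "If ANC or total WBC counts are confirmed below the acceptable limits, the Medical Monitor will contact the treating investigator". (The same sentence speaks of a low total WBC, although the only WBC limit listed is an upper one.) The purpose given for that call is this: "request close monitoring for risk of serious infection and appropriate follow-up, at the discretion of the investigator".
- ALC below 200: "the investigator will discontinue investigational drug and then consult with the Medical Monitor".
- Any of four liver criteria, with no apparent alternative cause: "the investigational drug must be permanently discontinued".

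On when a laboratory change counts as an adverse event, Section 9.2.6 says: "Clinically significant changes, in the judgment of the investigator, in laboratory parameters (abnormalities) will be recorded as AEs".

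**The concern.** A site cannot apply a count-based grade to a count that it does not see. It depends on the alert, the confirmation notice and the Medical Monitor's contact. For lymphocytes and liver tests Section 9.2.6 tells the site to stop. For neutrophils it describes monitoring only and does not point back to Section 8.1. An investigator who follows 9.2.6 as written could reasonably conclude that a low ANC is something to watch, while 8.1 may already require a stop.

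At stake is whether a mandatory safety stop is applied, and applied alike across sites. The protocol attributes an immunosuppressive mechanism to both agents and relies on laboratory monitoring to limit infection risk (Sections 3.3.1 and 3.3.2). It also holds participants in follow-up until ANC exceeds 1500/µL (Section 5.1.3), so it already treats ANC as relevant to safety.

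**Working it through.** The plan gives no figure to reproduce. The check sets the sections side by side and then works through the one threshold that the documents leave unprinted.

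**1. Does the 8.1 bullet reach neutrophils?** The term is undefined, so this is an inference. An exception for a lymphocyte count makes sense only if blood counts are otherwise covered, and no other count is excepted. Neutrophils therefore fall inside on the natural reading.

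**2. What is the site told to do?**

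| Trigger | Section 8.1 | Section 9.2.6 |
|---|---|---|
| Confirmed ALC < 200/µL | Must stop | Stop, then consult |
| Liver criteria (four) | Must stop (its own transaminase and bilirubin bullet) | Permanent stop |
| Confirmed ANC < 1000/µL | Must stop if a Grade 2 or higher bone marrow event | Monitor; follow-up at discretion; no reference to 8.1 |

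**3. Does another section supply the link?** The other ANC values are the entry limit (the lower of the lower limit of normal or 1500/µL, Section 6.2) and the discharge threshold (above 1500/µL, Section 5.1.3 and the footnote to Table 2-3). Neither is a stopping value. DMC laboratory review (Section 5.1.4), unscheduled haematology (Table 2-3) and the instruction to discuss immediate safety concerns with the sponsor (opening of Section 9) do not state an ANC stop either.

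**4. How far do the sections diverge?** Let L be the ANC below which CTCAE v5.0 assigns Grade 2 or higher. The documents do not print L, so it is treated as an assumption and varied around the alert level of 1000/µL.

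- L < 1000: the divergence covers confirmed counts below L. For confirmed counts from L up to 1000, monitoring alone is consistent with 8.1.
- L = 1000: the divergence covers every confirmed ANC alert.
- L > 1000: it covers every confirmed alert, and counts from 1000 up to L reach Grade 2 with no alert at all. The silent band is L − 1000 wide. Purely as an illustration, if L equalled the 1500/µL used elsewhere in the protocol, the band would be 1500 − 1000 = 500 cells/µL.

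Some divergence remains in every case. The unalerted band exists only in the third.

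**The case against.** The strongest defence is that both sections can be followed at once. Section 8.1 states when to stop, and 9.2.6 describes how blinded counts are escalated. A site can take the call, monitor closely, and stop if 8.1 is met. Nothing in 9.2.6 says that treatment continues, and its discretion wording concerns follow-up. The triggers also differ: 8.1 acts on an adverse event, 9.2.6 on a laboratory number, and investigator judgment turns one into the other. Citing a versioned grading scale is itself a specified criterion. ALC has its own stop because it is a known pharmacodynamic effect and is carved out of the general bullet, whereas ANC is not carved out and stays under the general rule. In an alerted case the investigator does know the parameter and its bound. Finally, 8.1 also requires a stop for any laboratory abnormality that the investigator thinks makes continuing unwise, and the sponsor discussion in Section 9 is expressly about whether to continue.

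Most of this stands, and it rules out several stronger readings. A reader might infer that the sections give opposing orders, or that 9.2.6 exempts neutrophils from 8.1. The text supports neither, since 9.2.6 does not override 8.1 or forbid stopping. A reader might infer that Grade 2 counts certainly go unalerted. That needs L above 1000/µL, which the documents cannot show. A reader might take the contrast with the ALC and liver rules as a measure of risk. It compares wording and says nothing about how often a low ANC occurs.

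The defence does not supply the missing link. The judgment it relies on concerns a blinded result and is prompted by a contact whose described content is monitoring. Section 9.2.6 does not say that the grade, or the 8.1 criterion, is conveyed. The actual text of the alert notice is not in the documents.

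**Conclusion.** The point holds as a gap between two sections, not as a formal contradiction. A mandatory stop is stated in 8.1, and the one described route that could trigger it for neutrophils does not carry it, so it can be missed or applied differently from site to site. If L exceeds 1000/µL, some qualifying counts would also raise no alert.

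The number of participants affected is unknown. The documents give no neutropenia rate, and the Phase 1 summaries in Sections 3.2.1.5 and 3.2.2.5 report none. Severity is low to moderate. The point concerns participant safety and consistent conduct; it makes no claim about the efficacy analysis.

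The conclusion rests on two assumptions: that bone marrow events include neutropenia, and that the alert and Medical Monitor contact carry no stopping instruction beyond what 9.2.6 describes.

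**What to change.** In Section 9.2.6:

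- Have whoever reviews counts unblinded at the centre, or the Medical Monitor, grade a confirmed low ANC against CTCAE v5.0, and instruct the site to discontinue when the 8.1 criterion is met. The site needs the instruction, not the count, so the blind is kept.
- Set the ANC alert no lower than the 8.1 stopping level, and print that level.

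Alternatively, if monitoring alone is intended, except ANC from the 8.1 bullet as is done for ALC, and state a separate ANC stopping value there.

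The cost is a sentence or two of text. The downside is possibly a few more discontinuations, which 8.1 may already require, and, if the alert level is raised, some more alerts and repeat tests.
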